## **2.3. Benefit/Risk assessment**

GSK has included provisions in this trial to ensure participant's safety. Safety monitoring has been and will be conducted throughout this study by an unblinded Independent Data Monitoring Committee (IDMC) and by the Sponsor. The study includes the establishment of a surveillance system which may facilitate detection of respiratory tract infections, in particular lower respiratory tract **illness** (LRTIs) in infants enrolled in the study. Measures to suspend the study should a potential safety issue be identified are described in Section 8.2.3.

***In February 2022, the Independent Data Monitoring Committee (IDMC) for the RSV MAT-009 study observed an imbalance in the proportion of preterm births in the active versus the placebo group and recommended that study enrollment be paused. As a result, GSK voluntarily paused the enrollment, randomization, and vaccination of participants in its active pregnant women studies to investigate this safety signal.***

***Following a review of additional unblinded data from the RSV MAT-009 study, the imbalance in preterm births was noted to persist across a range of risk factors. A higher proportion of neonatal deaths reported in the active group compared to the placebo group was also observed. GSK then decided to stop enrollment and vaccination in all ongoing trials of RSV Maternal Vaccine (RSVPreF3) as a precautionary measure.***

***The observed numerical imbalance in neonatal deaths is not an independent safety signal but a consequence of the validated signal of preterm birth. No numerical imbalance in neonatal deaths was observed in the cohort of infants born at term. An in-depth qualitative review of the clinical information available for each neonatal death concluded that the events leading to neonatal death (e.g., very low or low birth weight, sepsis, necrotizing colitis, pneumonia, respiratory distress syndrome, hypoxic-ischemic injury) are commonly observed in preterm-born infants, particularly those who are extremely and very preterm, and there is no consistent temporal pattern of events from birth or from maternal vaccination.***

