
To evaluate the occurrence of neonatal AEs of special interest (reported up to 6 weeks after birth), in infants born to mothers who were vaccinated with a single IM dose of the RSV Maternal vaccine.
	
The occurrence of neonatal AEs of special interest (reported up to 6 weeks after birth). These include small for gestational age, low birth weight including very low and extremely low birth weight (<2500 g, <1500g, <1000g), congenital anomalies (major external structural defects, internal structural defects, functional defects), neonatal death (in an extremely pre-term birth [22≤GA<28 weeks], in a preterm live birth [28≤GA<37 weeks], or in a term live birth), preterm birth.

Tertiary objectives:
 
CCI
	

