**Tertiary objectives:**

CCI

 By “medically assessed” it is meant that the infant was evaluated by a healthcare professional (physician, nurse, etc) for the lower respiratory tract illness.

Case definitions for *RSV-associated medically attended RTIs (RSV-MA-RTIs)*, RSV associated LRTIs and surveillance for potential LRTIs are briefly summarized in Section 4.2.6.

An infant is defined as a child younger than 1 year of age; a neonate is defined as an infant 28 days old or less.

Maternal and neonatal AESI and pregnancy outcomes should be recorded in the eCRF along with assessment of level of diagnostic certainty by GAIA definitions when applicable. Of note, some events of interest fall under a single category but have multiple subcategories. For example, hypertensive disorders of pregnancy is an event with three subcategories that include: 1) gestational hypertension; 2) pre-eclampsia; and 3) pre-eclampsia with severe features (including eclampsia). For each event, the investigator should identify the event and select the applicable sub-category.

The following adverse events are listed by GAIA as events of interest, but will not, for purposes of this study, be reported as AESIs. If any of these events meets the definition for an SAE, the event should be reported as such in the eCRF and the SAE narrative should contain enough information to permit assessment of level of diagnostic certainty by GAIA criteria:

Pregnancy-related: antenatal bleeding (morbidly adherent placenta, placental abruption, cesarean scar pregnancy, uterine rupture), postpartum hemorrhage, non-reassuring fetal status, oligohydramnios, polyhydramnios, gestational liver disease (intrahepatic cholestasis of pregnancy, acute fatty liver of pregnancy), maternal sepsis.

Neonatal: neonatal encephalopathy, congenital microcephaly (postnatally or prenatally diagnosed), neonatal infections (blood stream infections, meningitis, respiratory infection), respiratory distress in the neonate, failure to thrive, large for gestational age, macrosomia.

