### 10.3.5. Adverse events of special interest (AESIs)

AESIs include:

- The following pregnancy-related adverse events of special interest (newly occurring):
    - maternal death,
    - hypertensive disorders of pregnancy:
      - gestational hypertension,
      - pre-eclampsia,
      - pre-eclampsia with severe features including eclampsia,
    - fetal growth restriction,
    - pathways to preterm birth:
      - premature preterm rupture of membranes,
      - preterm labor,
      - provider-initiated preterm birth,
    - gestational diabetes mellitus, and
    - chorioamnionitis.
  - The following neonatal adverse events of special interest:
    - small for gestational age,
    - low birth weight including very low and extremely low birth weight (<2500 g, <1500 g, <1000 g),
    - congenital anomalies:
      - major external structural defects,
      - internal structural defects,
      - functional defects,
    - neonatal death:
      - in an extremely pre-term birth [22≤GA<28 weeks],
      - in a preterm live birth [28≤GA<37 weeks], or
      - in a term live birth,
- and
- preterm birth.

Refer to Section 8.3.4 for additional information about categorizing and reporting congenital anomalies.

Note: Worsening, post study vaccine administration, of pre-existing conditions already present at the time of enrolment. (eg. controlled gestational hypertension or controlled gestational diabetes) will be collected as (S)AEs and indicated as “worsening” or “aggravated” . These are not to be considered as AESIs.

When there is enough evidence to make any of the above diagnoses, the AE must be reported as AESI. Symptoms, signs or conditions which might (or might not) represent the above diagnoses, should be recorded and reported as AEs but not as AESI until the final or definitive diagnosis has been determined, and alternative diagnoses have been eliminated or shown to be less likely.

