**Table 43 Neonatal Death**

Death of a live born infant regardless of gestational age at birth, within the first 28 completed days of life

Levels of Diagnostic Certainty (1 highest level to 4 lowest level of certainty)	
Neonatal death in a non-viable live birth	
Level	Description
1	Live born infant AND 
 
• Gestational age <22 weeks (GA level of certainty = 1)
 
OR
 
• Birth weight <500 g
 
 AND Death of infant in first 28 days of life AND Medically-confirmed death
2	Live born infant AND Gestational age/size of newborn assessed as at least one of: 
 
• Gestational age <22 weeks (GA Level of Certainty = 1 OR 2)
 
• Birth weight <500 g
 
 AND Death of infant in first 28 days of life AND Medically-confirmed death OR non-medically-confirmed death
3	Live born infant AND Gestational age <5 months according to parent/family member/delivery attendant (GA Level of Certainty = 2 OR 3) AND Death of infant in first 28 days of life AND Medically-confirmed death OR non-medically-confirmed death
Neonatal death in an extremely preterm live birth	
Level	Description
1	Live born infant AND 
 
• Gestational age ≥22 and <28 weeks (GA Level of Certainty = 1)
 
OR
 
• Birth weight ≥500 g but <1000 g
 
 AND Death of infant in first 28 days of life AND Medically-confirmed death
2	Live born infant AND Gestational age/size of newborn assesses as one or more of: 
 
• Gestational age ≥22 and <28 weeks (GA Level of Certainty = 1 OR 2)
 
• Birth weight ≥500 g but <1000 g
 
 AND Death of infant in first 28 days of life AND Medically-confirmed death OR non-medically-confirmed death

Levels of Diagnostic Certainty (1 highest level to 4 lowest level of certainty)	
Neonatal death in an extremely preterm live birth (continued)	
Level	Description
3	Live born infant AND Gestational age $\geq 5$ months but $< 7$ months according to neonate's parent (mother/father)/family member/delivery attendant (GA Level of Certainty = 2 OR 3) AND Death of infant in first 28 days of life AND Medically-confirmed death OR non-medically-confirmed death
Neonatal death in a preterm live birth (gestational age <math>\geq 28</math> to <math>< 37</math> weeks)	
Level	Description

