1	Live born infant AND 
 
• Gestational age <math>\geq 28</math> and <math>< 37</math> weeks (Level of Certainty = 1)
 
OR
 
• Birth weight <math>\geq 1000</math> g but <math>< 2500</math> g
 
 AND Death of infant in first 28 days of life AND Medically-confirmed death
2	Live born infant AND Gestational age/size of newborn assesses as one or more of: 
 
• Gestational age <math>\geq 28</math> and <math>< 37</math> weeks (GA Level of Certainty = 1 OR 2)
 
• Birth weight <math>\geq 1000</math> g but <math>< 2500</math> g
 
 AND Death of infant in first 28 days of life AND Medically-confirmed death OR non-medically-confirmed death
3	(MAY apply to LMIC- or may be non-viable in LMIC) Live born infant AND Gestational age $\geq 7$ months but $< 9$ months according to parent/family member/delivery attendant (GA Level of Certainty = 2 OR 3) AND Death of infant in first 28 days of life AND Medically-confirmed death OR non-medically-confirmed death
Neonatal death in a term live birth	
Level	Description
1	Live born infant AND Gestational age $\geq 37$ weeks (GA Level of Certainty = 1) AND 
 
• Birth weight <math>> 2500</math> g
 
OR
 
• Documented intra-uterine growth retardation if <math>\leq 2500</math> g
 
 AND Death of infant in first 28 days of life AND Medically-confirmed death

Levels of Diagnostic Certainty (1 highest level to 4 lowest level of certainty)	
Neonatal death in a term live birth (continued)	
Level	Description
2	Live born infant AND Gestational age/size of newborn assesses as one or more of: 
 
• Gestational age <math>\geq 37</math> weeks (GA Level of Certainty = 1 OR 2)
 
• Birth weight <math>\geq 2500</math> g
 
 AND Death of infant in first 28 days of life AND Medically-confirmed death OR non-medically-confirmed death which is confirmed by examination by (by at least) non-medically-trained attendant (e.g. undertaker, community member)
3	(apply to Lower Middle Income Countries) Live born infant AND 2. Gestational age $\geq 9$ months according to parent/family member/delivery attendant (GA Level of Certainty = 2 OR 3) AND 3. Death of infant in first 28 days of life AND 4. Medically-confirmed death OR non-medically-confirmed death

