**Table 46 Preterm Birth**

Birth in less than 37 gestation-completed weeks (less than 259 days).

Prematurity and assessment of gestational age	
Level	Description
1	Certain last menstrual period date (LMP) LMP or intrauterine insemination (IUI) date or embryo transfer (ET) date with confirmatory 1st trimester scan ( $\leq 13^{6/7}$ weeks). OR 1st trimester scan ( $\leq 13^{6/7}$ weeks)
2a	Certain LMP* with 2nd trimester scan ( $14^{0/7}$ weeks to $27^{6/7}$ weeks). Note: If LMP and U/S do not correlate, default to U/S GA assessment. OR Certain LMP* with 1st trimester physical examination.
2b	Uncertain LMP with 2nd trimester scan ( $14^{0/7}$ weeks to $27^{6/7}$ weeks).
3a	Certain LMP with 3rd trimester scan $\geq 28^{0/7}$ weeks OR Certain LMP with confirmatory 2nd trimester Fundal Height (FH) OR Certain LMP with birth weight OR Uncertain LMP with 1st trimester physical examination.
3b	Uncertain LMP with FH. OR Uncertain LMP with newborn physical assessment. OR Uncertain LMP with Birth weight
*	Definitions of LMP, birth weight and physical assessment in referenced article.

Reference: Quinn JA, Munoz FM, Gonik B, et al. Preterm birth: Case definition & guidelines for data collection, analysis, and presentation of immunization safety data. *Vaccine*. 2016;34(49):6047-6056.

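### Table 43 lets birth weight stand in for gestational age when neonatal deaths are sub-categorised, so one death can fit two classes of an endpoint defined by gestational age

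*Protocol*

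**What the plan says.** Protocol Table 4 gives the secondary safety endpoint as "neonatal death (in an extremely pre-term birth [22≤GA<28 weeks], in a preterm live birth [28≤GA<37 weeks], or in a term live birth". Section 10.3.5 repeats the bands in the AESI list ("in an extremely pre-term birth [22≤GA<28 weeks" and "in a preterm live birth [28≤GA<37 weeks"), and SAP Table 1 and SAP 5.4.1 carry them over. Two classes are set by gestational age alone; term is what remains.

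Appendix 9 introduces its tables as giving both the event definitions and the certainty levels, and names Table 43 for neonatal death. Table 43 works differently from the endpoint:

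- Extremely preterm, Levels 1 and 2: the gestational-age band, or the weight band "Birth weight ≥500 g but <1000 g".
- Preterm, Levels 1 and 2: the gestational-age band, or 1000 g to under 2500 g. The heading of this block states a gestational-age band only.
- Term, Level 2: 37 weeks or more, or 2500 g or more. Term Level 1 is stricter. It requires 37 weeks or more, plus either a weight above 2500 g or documented growth restriction.
- Non-viable: under 22 weeks, or under 500 g. The endpoint has no such class.

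The Level 2 connector is "Gestational age/size of newborn assesses as one or more of". Footnote 4 to Table 4 leaves the choice to the site: "For each event, the investigator should identify the event and select the applicable sub-category".

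**The concern.** A sub-category endpoint is interpretable only if each event has one class and everyone assigns it by the same variable. Here the endpoint uses gestational age, while the table handed to the investigator uses gestational age or weight. Small-for-age and large-for-age infants are where the two disagree, and small infants are a group in which neonatal deaths are to be expected. Two sites could file identical deaths differently, or one site could follow the highest certainty level into a class that contradicts the endpoint. The count of neonatal deaths would be right, but the distribution over extremely preterm, preterm and term might not be.

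**Working it through.** There is no sample size or error rate to reproduce. The check applies Table 43 as written to example infants and compares the result with the endpoint class. Inputs are the endpoint bands (Table 4, Section 10.3.5), the Table 43 criteria, and the dating-certainty levels in Section 10.8.1. All deaths are taken as medically confirmed.

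In Table 43 the gestational-age route needs dating certainty 1 for Level 1, and certainty 1 or 2 for Level 2. The weight route needs no dating certainty. Level 3 uses gestational age in months as reported by family or the delivery attendant.

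| Infant | Dating certainty | Endpoint class | Table 43 matches |
|---|---|---|---|
| 29 wk, 950 g | 1 | preterm | extremely preterm Level 1 (weight); preterm Level 1 (age) |
| 27 wk, 1050 g | 1 | extremely preterm | extremely preterm Level 1 (age); preterm Level 1 (weight) |
| 38 wk, 2300 g | 1 | term | preterm Level 1 (weight); term Level 2 (age), or term Level 1 if growth restriction is documented |
| 35 wk, 2600 g | 1 | preterm | preterm Level 1 (age); term Level 2 (weight) |
| 24 wk, 480 g | 1 | extremely preterm | non-viable Level 1 (weight); extremely preterm Level 1 (age) |
| 38 wk, 2300 g | 3A | term | preterm Level 1 (weight); term no higher than Level 3 |
| 36 wk, 2600 g | 3A | preterm | term Level 2 (weight); preterm no higher than Level 3 |

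The 3A rows can occur. Section 5.1.1 accepts a certain last menstrual period corroborated by ultrasound after 28 weeks, and Section 10.8.1 marks that combination (Level 3A) as applicable for enrolment.

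The non-viable class can in practice be entered only by weight. Vaccination is at 24 weeks 0 days or later, so a correctly enrolled pregnancy cannot deliver before 22 weeks.

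A grid confirms that the overlap is structural. Take 19 completed weeks (24 to 42) by 84 weights (400 to 4550 g in 50 g steps): 19 × 84 = 1596 cells. Age and weight agree in:

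- extremely preterm: 4 weeks × 10 weights = 40
- preterm: 9 × 30 = 270
- term: 6 × 42 = 252

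The total is 562, leaving 1596 − 562 = 1034 discordant cells. At dating certainty 1 or 2, each of these meets two classes. At certainty 3, each meets one class at Levels 1–2, and it is not the endpoint class. The grid gives every cell equal weight, including implausible ones, so it shows that conflicts exist and not how often they would arise.

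Under gestational age alone, every infant falls in exactly one class.

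**The case against.** The best reply is that the term/preterm comparison is already safe. SAP 5.4.1 summarises neonatal AESIs by gestational age at birth (37 weeks or more against under 37), SAP Section 8 confirms it, and neither depends on Table 43. That stands, and it removes the largest potential consequence. It does not govern the sub-category tabulation, and it does not separate extremely preterm from preterm.

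Second, the endpoint names carry their bands, and footnote 4 treats diagnostic certainty as a separate attribute. A careful investigator would not select a 28-to-37-week label for a 38-week infant. This is a fair reading, but Appendix 9 presents Table 43 as a definition too, and no visible text says which source prevails.

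Third, the analysis-method cells for neonatal AESIs are redacted and the table specifications sit in a separate document, so a precedence rule may exist out of view. The point is limited to what can be read.

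A reader might go further in three ways that the documents do not support:

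- That the sponsor's statement in Section 2.3, "No numerical imbalance in neonatal deaths was observed in the cohort of infants born at term", rests on weight-based filing. The text does not say how that cohort was formed, and it also cites a qualitative review of each death.
- That the sub-categories were chosen by unblinded staff. Section 6.3.6 places site unblinding after the decision to stop, whereas Section 2.3 has the neonatal-death imbalance observed before that decision.
- That Table 46 has the same flaw because it lists rows such as "Uncertain LMP with newborn physical assessment". Table 46 defines preterm birth by gestational age alone (under 259 days). Those rows grade certainty, and that one is not among the combinations accepted for enrolment.

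**Conclusion.** The contradiction holds in a limited form. Table 43 lets weight replace gestational age at Levels 1–2 for the extremely preterm and preterm classes and at Level 2 for term, against an endpoint built on gestational-age bands. The same death can meet two classes, and with Level 3A dating the highest-certainty match can be the wrong one. The affected output is the neonatal-death tabulation by investigator-selected sub-category, including the 28-week boundary and the unmatched non-viable class. Total neonatal deaths do not change.

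Misfiling can go either way: the 38-week, 2300 g infant drifts from term to preterm, and the 36-week, 2600 g infant with Level 3A dating from preterm to term. The documents give no sub-category counts and no weight distribution among deaths, so neither the number affected nor the net direction can be stated. The conclusion assumes that no precedence rule sits in the redacted cells or the separate table specifications.

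**What to change.** Add one derivation rule to the SAP. Assign the neonatal-death sub-category from the gestational age at delivery already used in SAP 5.1.1 and 5.4.1, as mutually exclusive classes: 22 to under 28 weeks, 28 to under 37 weeks, and 37 weeks or more. State that Table 43 supplies only the level of diagnostic certainty, and that deaths meeting its non-viable class by weight are classed by gestational age like any other. Name the gestational-age variable in the rule, since SAP 9.1 covers only gestational age at vaccination.

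Add a listing of deaths whose investigator-selected sub-category differs from the derived one. The cost is a short paragraph and one listing. No new data are needed: gestational age at delivery is already a planned summary variable, and the investigator's selection is recorded in the eCRF.

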**Table 44 Neonatal Infections**

Neonatal bacteremia and sepsis (of early or late onset), meningitis, pneumonia and other respiratory infections such as bronchiolitis, caused by bacteria, parasites, viruses or fungi. Localized eye and ear infections, encephalitis, urinary tract infections and intestinal infections were excluded from these guidelines

Neonatal invasive blood stream infections: bacterial/fungal/viral	
Level	Description
1	Recognized pathogen identified using a validated method and from a normally sterile site.
2	Not meeting Level 1 of evidence AND Meeting 3 or more of the following criteria: Temperature $\geq 37.5$ °C or $< 35.5$ °C Tachycardia or new or more frequent episodes of bradycardia New or more frequent episodes of apnea or increased oxygen requirement or increased requirement for ventilatory support Lethargy or moving only when stimulated or hypotonia or irritability Difficulty in feeding or abdominal distention Pallor or poor perfusion or hypotension Abnormal White Cell Count or I/T ratio $> 0.2$ Abnormal platelet count Increased inflammatory markers (CRP, procalcitonin) Metabolic acidosis as defined by a base excess
3	Not meeting Level 1 or 2 of evidence AND Meeting 2 or more of the following criteria: Temperature $\geq 37.5$ °C or $< 35.5$ °C Tachypnea or severe chest in drawing or grunting or cyanosis Change in level of activity History of feeding difficulty History of convulsions

Bacterial/fungal/viral meningitis	
Level	Description
1	Recognized pathogen identified using a validated method from cerebrospinal fluid (CSF)
2	CSF pleocytosis OR positive IgM antibodies to a specific pathogen in the CSF AND Recognized pathogen identified using a validated method from a normally sterile site (other than CSF) AND Temperature $\geq 37.5$ °C or $< 35.5$ °C AND 1 or more criteria below: History of convulsions Lethargy or irritability Coma Apnea Bulging fontanel Neck stiffness
3a	CSF pleocytosis AND No pathogen identified using a validated method from a normally sterile site AND Temperature $\geq 37.5$ °C or $< 35.5$ °C AND 3 or more criteria below: History of convulsions Lethargy or irritability Coma Apnea Bulging fontanel Neck stiffness
3b	No lumbar puncture done or no sample available AND Temperature $\geq 37.5$ °C or $< 35.5$ °C AND 4 or more criteria below: History of convulsions Lethargy or irritability Coma Apnea Bulging fontanel Neck stiffness

Respiratory bacterial/fungal/viral infection	
Level	Description
1	
New or progressive or persistent infiltrate or shadowing or fluid in the intrapleural cavity or interlobar fissure on chest X-ray AND
 
 
• Recognized virus identified using a validated assay from an upper respiratory sample OR
 
• Recognized pathogen identified using a validated method and from a normally sterile site
 
 
AND
 
3 or more criteria below: Temperature <math>\geq 37.5</math> °C or <math>< 35.5</math> °C Tachypnea or Nasal flaring or Chest in-drawing or Grunting Desaturations or increased oxygen requirements or increased ventilator requirements or oxygen saturation <math>< 95\%</math> Apneas Increased respiratory secretions or Increased suctioning requirements Cough or wheeze or crepitations Increased CRP or procalcitonin

2	
New or progressive or persistent infiltrate or shadowing or fluid in the intrapleural cavity or interlobar fissure on chest X-ray AND
 
4 or more criteria below: Temperature <math>\geq 37.5</math> °C or <math>< 35.5</math> °C Tachypnea or Nasal flaring or Chest in-drawing or Grunting Desaturations or increased oxygen requirements or increased ventilator requirements or oxygen saturation <math>< 95\%</math> Apneas Increased respiratory secretions or Increased suctioning requirements Cough or wheeze or crepitations Increased CRP or procalcitonin

3	
2 or more criteria below: Difficulty in breathing/Tachypnea Severe chest in-drawing Nasal flaring Grunting Wheezing Stridor Fever

Reference: Vergnano S, Buttery J, Cailles B, et al. Neonatal infections: Case definition and guidelines for data collection, analysis, and presentation of immunization safety data. *Vaccine*. 2016;34 (49):6038-6046

